9.1.1 Causality (Attribution) of Adverse Events

The investigator is to assess the causal relation of all AEs (i.e., whether there is a reasonable possibility that the study drug caused the event) using the following definitions:

Not Related: Another cause of the AE is more plausible; a temporal sequence cannot be established with the onset of the AE and administration of the investigational product; or, a causal relationship is considered biologically implausible.

Unlikely: The current knowledge or information about the AE indicates that a relationship to the investigational product is unlikely.

Possibly Related: There is a clinically plausible time sequence between onset of the AE and administration of the investigational product, but the AE could also be attributed to concurrent or underlying disease, or the use of other drugs or procedures. Possibly related should be used when the investigational product is one of several biologically plausible AE causes.

Probably Related: The AE is likely related to investigational product.

Definitely Related: The AE is clearly related to use of the investigational product.

9.2 Serious Adverse Events

Serious adverse event (SAE) means any untoward medical occurrence that at any dose:

- Results in death.
- Is life threatening (Note: the term “life-threatening” refers to an event/reaction in which the patient was at risk of death at the time of the event/reaction. It does not refer to an event/reaction which hypothetically might have caused death if it were more severe).
- Requires inpatient hospitalization or prolongation of an existing hospitalization
- Results in persistent or significant disability or incapacity. (Disability is defined as a substantial disruption of a person’s ability to conduct normal life functions).
- Is a congenital anomaly/birth defect.
- Is a medically important event or reaction. Medical and scientific judgment should be exercised in deciding whether other situations should be considered serious, such as important medical events that might not be immediately life threatening or result in death or hospitalization, but might jeopardize the patient or might require intervention to prevent one of the other outcomes listed in the definition above.

9.3 Adverse Event Documentation

All AEs must be recorded on case report forms (CRFs). Documentation must be supported by an entry in the subject’s file. Each event should be described in detail along with start and stop dates, severity, relationship to investigational product as judged by the Investigator, action taken and outcome.

9.3.1 Adverse Events of Special Interest

AESIs are a subset of Events to Monitor (EtMs) of scientific and medical concern specific to the atezolizumab, for which ongoing monitoring and rapid communication by the Investigator to the Genentech is required. Such an event might require further investigation in order to characterize and understand it. Depending on the nature of the event, rapid communication by the Sponsor-Investigator to other parties (e.g., Regulatory Authorities) may also be warranted.

The following AEs are considered of special interest and must be reported to the Genentech Drug Safety expeditiously, irrespective of regulatory seriousness criteria:

- Cases of potential drug-induced liver injury that include an elevated ALT or AST in combination with either an elevated bilirubin or clinical jaundice, as defined by Hy's Law and based on the following observations:
 - Treatment-emergent ALT or AST $> 3 \times$ ULN (or $> 3 \times$ baseline value in disease states where LFTs may be elevated at baseline) in combination with total bilirubin $> 2 \times$ ULN (of which $\geq 35\%$ is direct bilirubin)
 - Treatment-emergent ALT or AST $> 3 \times$ ULN (or $> 3 \times$ baseline value in disease states where LFTs may be elevated at baseline) in combination with clinical jaundice
- Data related to a suspected transmission of an infectious agent by the study treatment, as defined below
 - Any organism, virus, or infectious particle (e.g., prion protein transmitting transmissible spongiform encephalopathy), pathogenic or non-pathogenic, is considered an infectious agent. A transmission of an infectious agent may be suspected from clinical symptoms or laboratory findings that indicate an infection in a patient exposed to a medicinal product. This term applies only when a contamination of study treatment is suspected.
- Systemic lupus erythematosus
- Events suggestive of hypersensitivity, infusion-related reactions, cytokine-release syndrome, macrophage activating syndrome, hemophagocytic lymphohistiocytosis
- Nephritis
- Ocular toxicities (e.g., uveitis, retinitis, optic neuritis)
- Grade ≥ 2 cardiac disorders (e.g., atrial fibrillation, myocarditis, pericarditis)
- Vasculitis
- Autoimmune hemolytic anemia
- Severe cutaneous reactions (e.g., Stevens-Johnson syndrome, dermatitis bullous, toxic epidermal necrolysis)
- Myelitis
- Facial paresis

9.4 Methods and Timing for Assessing and Recording Safety Variables

The investigator is responsible for ensuring that all AEs and SAEs that are observed or reported during the study, are collected and reported to the FDA, appropriate IRB(s), and Genentech, Inc. in accordance with CFR 312.32 (IND Safety Reports).

9.4.1 Adverse Event Reporting Period

The study period during which all AEs and SAEs must be reported beginning at initiation of study treatment until 30 days following the last administration of study treatment or study discontinuation/termination, whichever is earlier. After this period, investigators should only report SAEs that are attributed to prior study treatment.

Investigators will seek information on adverse events at each patient contact. All adverse events, whether reported by the patient or noted by study personnel, will be recorded in the patient's medical record.

Assessment of Adverse Events

All AEs and SAEs whether volunteered by the patient, discovered by study personnel during questioning, or detected through physical examination, laboratory test, or other means will be reported appropriately. Each reported AE or SAE will be described by its duration (i.e., start and end dates), regulatory seriousness criteria if applicable, suspected relationship to atezolizumab (see following guidance), and actions taken.

To ensure consistency of AE and SAE causality assessments, investigators should apply the following general guideline:

Yes

There is a plausible temporal relationship between the onset of the AE and administration of atezolizumab, and the AE cannot be readily explained by the subject's clinical state, intercurrent illness, or concomitant therapies; and/or the AE follows a known pattern of response to atezolizumab or with similar treatments; and/or the AE abates or resolves upon discontinuation of atezolizumab or dose reduction and, if applicable, reappears upon re-challenge.

No

Evidence exists that the AE has an etiology other than atezolizumab (e.g., preexisting medical condition, underlying disease, intercurrent illness, or concomitant medication); and/or the AE has no plausible temporal relationship to atezolizumab administration (e.g., cancer diagnosed 2 days after first dose of atezolizumab).

Expected adverse events are those adverse events that are listed or characterized in the Package Insert (P.I) or current Investigator Brochure (I.B).

Unexpected adverse events are those not listed in the P.I. or current I.B or not identified. This includes adverse events for which the specificity or severity is not consistent with the description in the P.I. or I.B. For example, under this definition, hepatic necrosis would be unexpected if the P.I. or I.B. only referred to elevated hepatic enzymes or hepatitis.

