6. STUDY CALENDAR

Neoadjuvant Calendar:

Evaluation	Initial Screen ⁴ ≤28d prior to 1 st cycle	Patient Enrolled (0 Day)	Week 1 Neoadjuvant cycle 1 (±3d)	Week 4 Neoadjuvant cycle 2 (±3d)	Week 6 Post-neo-adjuvant: Imaging & Safety (±10d)	Surgery ¹
Inclusion/Exclusion Criteria	X					
Demographics	X					
Medical History	X					
Weight and Vital Signs	X		X	X	X	
Atezolizumab			X	X		
MRI or CT Head and Neck	X				X	
PET	X					
Blood Collection ⁵	X		X	X	X	X
Tissue Collection ⁵	X					X
Physical Exam	X		X	X	X	
Urinalysis	X					
Pregnancy Test	X					
Adverse Events			X	X		X

Adjuvant Calendar: Patient with pCR at time of surgery

Evaluation	Post-surgery Visit 1 week (±3d)	Post-surgery Visit 1 month (±14d)	Surveillance Follow Up Every 3 mo to 3 years (±14d)
Inclusion/Exclusion Criteria			
Demographics			
Medical History			
Weight and Vital Signs	X	X	X
Atezolizumab			
MRI or CT Head and Neck			
PET			X ²
Blood Collection ⁵			X
Tissue Collection ⁵			
Physical Exam	X	X	X
Pregnancy Test			
Adverse Events	X	X	

Adjuvant Calendar: Patient with residual disease at time of surgery

Evaluation	Post-surgery Visit 1 week ($\pm 3d$)	Post-surgery Visit 1 month ($\pm 14d$)	Adjuvant Cycle #1 ⁶ < 7 wks post-op		Adjuvant Cycle #2 +3W ($\pm 3d$)		Adjuvant Cycles #3 - #15 +3W ($\pm 3d$)	Surveillance Follow Up Every 3 mo to 3 yr ³ ($\pm 14d$)
			Weeks					
			1	2	3	4	5	6
Inclusion/Exclusion Criteria								
Demographics								
Medical History								
Weight and Vital Signs	X	X	X		X		X	X
Atezolizumab			X		X		X	
MRI or CT Head and Neck								
PET								X ²
Blood Collection ⁵			X		X		X	X
Tissue Collection ⁵								
Physical Exam	X	X	X		X		X	X
Urinalysis								
Pregnancy Test			X		X		X	
Adverse Events	X	X	X		X		X	X ⁷
Atezolizumab 1200 MG			X		X		X	
Adjuvant Radiation			X X X X X X					

1. Surgery must be completed within 10 weeks after patient is enrolled.
2. Only performed at 3mo follow up visit per standard of care.
3. If the patient is unable to attend the standard of care office appointment they will be contacted via video or phone visit.
4. Any screening assessments performed within 28 days prior to the consent signing can be accepted.
5. See section 5.1.5.
6. Start adjuvant therapy more than 4 weeks after and within 7 weeks after surgery per SOC.
7. AE monitoring at first surveillance visit only ≥ 30 days following last dose of Atezolizumab

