9.1 Adverse Event Definition

Any patient enrolled in the trial who signed the consent form and received at least one dose of atezolizumab will be eligible for adverse event reporting. Only laboratory abnormalities that result in signs or symptoms that require intervention or follow up and are considered clinically significant should be recorded as AEs. All other AEs whether serious or non-serious will be entered into the institutional database from the time of first protocol intervention up until 30 days after the last dose of study drugs. The Principal Investigator or designee will be responsible for assigning attribution to the study treatment.

This includes the following:

- AEs not previously observed in the subject that emerge during the protocol-specified AE reporting period, including signs or symptoms associated with squamous cell carcinoma that were not present prior to the AE reporting period.
- Complications that occur as a result of protocol-mandated interventions (e.g., invasive procedures such as cardiac catheterizations)
- If applicable, AEs that occur prior to assignment of study treatment associated with medication washout, no treatment run-in, or other protocol-mandated intervention.
- Preexisting medical conditions (other than the condition being studied) judged by the

investigator to have worsened in severity or frequency or changed in character during the protocol-specified AE reporting period.

The descriptions and grading scales found in the revised NCI Common Terminology Criteria for Adverse Events (CTCAE) version 5.0 will be utilized for AE reporting. All appropriate treatment areas should have access to a copy of the CTCAE version 5.0. A copy of the CTCAE version 5.0 can be downloaded from the CTEP web site

http://ctep.cancer.gov/protocolDevelopment/electronic_applications/ctc.htm.

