9.5.2.6 Post-Study Adverse Events

After the end of the adverse event reporting period (defined as 30 days after the last dose of study drug), the investigator should report all deaths (regardless of cause) and any serious adverse event including development of cancer or a congenital anomaly in a subsequently conceived offspring of a female subject who participated in the study that is believed to be related to prior exposure to study drug.

Case Transmission Verification (CTV) will be performed by both parties during this period to ensure successful transmission of Single case reports.

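### AE reporting closes 30 days after the last dose, before the nominal 1-month post-operative AE assessment in patients who receive no adjuvant atezolizumab

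*Combined protocol and SAP*

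**What the plan says.** Three sections set the end of AE reporting, and all count from the last dose.

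- Section 9.4.1: AEs and SAEs are reportable "until 30 days following the last administration of study treatment or study discontinuation/termination, whichever is earlier". It continues: "After this period, investigators should only report SAEs that are attributed to prior study treatment".
- Section 9.1: AEs are "entered into the institutional database from the time of first protocol intervention up until 30 days after the last dose of study drugs".
- Section 9.5.2.6, on what happens once the window has closed: "the adverse event reporting period (defined as 30 days after the last dose of study drug), the investigator should report all deaths", whatever the cause, together with SAEs believed related to earlier exposure.

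Section 9.4.1 also keeps elicitation open: "Investigators will seek information on adverse events at each patient contact", with findings written in the medical record.

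Two groups in Section 3.1 have a neoadjuvant dose as their last dose. Patients with pCR go straight to surveillance. Patients who progress and do not meet the continuation criteria stop after dose 1 and later receive radiation only. Surgery is at least two weeks after dose 2 and within 10 weeks of enrolment.

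The Section 6 calendar for pCR patients marks AE assessment 1 week (±3 days) and 1 month (±14 days) after surgery. The calendar for residual disease marks the same two visits, then every adjuvant cycle. Its footnote 7 ties a final AE check to at least 30 days after the last dose. The pCR calendar has no such link.

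**The concern.** For a pCR patient the window is counted from a dose given weeks before the operation, so it can close within days of surgery or even before it. The calendar still sends the patient to an AE assessment a month after surgery, and Section 3.1 has pCR patients assessed for treatment-related side effects during surveillance. What they report may be charted. But an event that starts after closure need not be reported or entered unless it is an SAE attributed to treatment or, under Section 9.5.2.6, a death.

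Secondary objective 3 is the safety of neoadjuvant atezolizumab in resectable disease, and the post-operative month is a central part of that question. A patient with residual disease who restarts atezolizumab remains inside the window over the same period. Required entry of post-operative AEs therefore depends on whether adjuvant drug follows, and so largely on pCR, the primary outcome. The descriptive AE tables in Section 10.1 would pool patients with unequal capture. With 18 patients a single event matters: 1/18 = 5.6% passes the 5% Tier 2 threshold for specific Grade 3 to 5 AEs and SAEs, and the second event (2/18 = 11.1%) passes the 10% threshold for any specific AE.

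**Working it through.** **Inputs.** Closure = last dose + 30 days (9.1, 9.4.1, 9.5.2.6). Surgery is at least 14 days after dose 2 and within 10 weeks of enrolment (3.1). Repeat imaging is in week 6 (Section 6), one week before surgery (3.1). Post-operative AE visits are as in Section 6.

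**Assumptions.** Enrolment and dose 1 on day 1; dose 2 on day 22; one month = 30 days.

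**Two doses.** Closure is day 22 + 30 = day 52. Earliest surgery is day 22 + 14 = day 36; the latest is about day 70. Week 6 imaging (days 36 to 42) plus 7 days gives surgery on days 43 to 49, called the nominal path below.

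| Surgery day | Closure, post-op day | 1-week visit minus closure | 1-month visit minus closure | Earliest allowed 1-month visit (surgery + 16) minus closure | Days covered of first 30 post-op |
|---|---|---|---|---|---|
| 36 | 16 | −9 | 14 | 0 | 16 |
| 43 | 9 | −2 | 21 | 7 | 9 |
| 46 | 6 | 1 | 24 | 10 | 6 |
| 49 | 3 | 4 | 27 | 13 | 3 |
| 52 | 0 | 7 | 30 | 16 | 0 |
| 70 | −18 | 25 | 48 | 34 | 0 |

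The 1-month column does not depend on the date of dose 2 as such:

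(surgery + 30) − (last dose + 30) = surgery − last dose ≥ 14 days.

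Moving dose 2 by its ±3 days (day 19, 22 or 25) leaves the minimum gap at 14 and gives a maximum, for surgery on day 70, of 51, 48 or 45 days. The nominal 1-week visit is outside from surgery day 46. The assessment at surgery is outside only if surgery is more than 30 days after dose 2. On the nominal path, 30 − 9 = 21 to 30 − 3 = 27 of the first 30 post-operative days are uncovered.

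**Length of month.** With a 28- to 31-day month the smallest nominal gap is 12 to 15 days. The whole ±14-day allowance lies after closure once surgery is 15 or more days after dose 2 (30-day month) or 17 or more days after it (28-day month).

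**One dose only.** Closure is day 1 + 30 = day 31. Surgery + 30 exceeds 31 for any surgery after day 1; surgery + 7 exceeds 31 from surgery day 25.

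**Comparison: residual disease, all 15 cycles, no delays.** Section 6, footnote 6: "Start adjuvant therapy more than 4 weeks after and within 7 weeks after surgery per SOC". Section 3.1 says less than 7 weeks, so adjuvant start is post-operative day 29 to 48. Cycle 15 is 14 × 21 = 294 days later, day 323 to 342. Adding 30 gives closure on post-operative day 353 to 372. All of the first 30 days are inside.

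**Number affected.** Expected pCR patients: 18 × 0.30 = 5.4 at the design rate; 18 × 0.05 = 0.9 at the null rate.

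**The case against.** The strongest reply is that other provisions carry no time limit. Section 9.3 requires every AE to be recorded on a CRF, and Section 9.4 makes the investigator responsible for collecting and reporting everything observed during the study. Both calendars mark the same two post-operative visits. On that reading capture is equal, and the documents merely need tidying. This does not hold up. Section 9.1 counts new AEs as those arising within the reporting period and limits database entry to it. Section 9.4 is the general introduction to the specific limit in 9.4.1. If 9.3 was meant to be unlimited, the contradiction still has to be resolved before the AE tables can be interpreted.

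A second reply is that a visit after closure is not itself a defect: it can pick up events that began earlier, and footnote 7 places such a visit at or after closure in the residual-disease calendar. That is fair. The count that matters is the post-operative days on which a new event need not be entered, which is why the table shows days covered as well as visit gaps.

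Three limits also stand. With surgery at its earliest and the 1-month visit at or very near its −14-day limit, the visit can reach the closure day, or 2 days inside it with a 28-day month. No calendar is given specifically for patients stopped after dose 1, and their number cannot be estimated from the documents. Related SAEs and deaths stay reportable, few pCR patients are expected, and the summary is descriptive.

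**Conclusion.** The concern holds. After two doses, the nominal 1-month post-operative AE assessment is after closure for every permitted surgery date, by 14 to 48 days (up to 51 if dose 2 is 3 days early). On the nominal path reporting closes on post-operative day 3 to 9. The result rests on the day-1 enrolment and 30-day-month assumptions, and on Sections 9.1 and 9.4.1 governing entry, as their wording indicates.

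The consequence is limited to non-serious AEs and unrelated non-fatal SAEs that start after closure, in about 5 of 18 patients at the design pCR rate plus any patients stopped after dose 1. The primary endpoint and the Simon rule are unaffected. It should be corrected because it makes the safety record for secondary objective 3 uneven in a way tied to pCR.

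Separately, Section 9.4.1 restricts later reports to SAEs attributed to treatment, while 9.5.2.6 requires all deaths. Those two sections contradict each other whatever the timing.

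**What to change.** - In Sections 9.1, 9.4.1 and 9.5.2.6, end the AE window at the later of 30 days after the last dose of atezolizumab and 30 days after surgery. Keep the current end point for patients who never have surgery or who withdraw.
- Collect AEs with onset up to that day at the scheduled 1-month visit, or at the next contact if that visit is early or missed. A visit as late as post-operative day 44 can still record onsets through day 30.
- In Section 10.1, summarise AEs from first dose to 30 days after surgery for all operated patients, so that pCR and residual-disease patients are compared over the same period.
- Reconcile 9.4.1 with 9.5.2.6 on deaths, and state whether the AEs of special interest in 9.3.1 remain reportable after the window.

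The cost is wording in three sections, a sentence in the analysis section, and a few more AE entries at visits already planned. No visits or procedures are added. The drawback is recall: if the 1-month visit takes place before post-operative day 30, the remaining days depend on what the patient remembers at the next contact.

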9.5 Procedures for Eliciting, Recording, and Reporting Adverse Events

9.5.1 Eliciting Adverse Event Information

A consistent methodology of non-directive questioning should be adopted for eliciting adverse event information at all patient evaluation timepoints. Examples of non-directive questions include the following:

"How have you felt since your last clinic visit?"

"Have you had any new or changed health problems since you were last here?"

9.5.2 Specific Instructions for Recording Adverse Events

Investigators should use correct medical terminology/concepts when reporting SAEs. Avoid colloquialisms and abbreviations.

9.5.2.1 Diagnosis versus Signs and Symptoms

If known at the time of reporting, a diagnosis should be reported rather than individual signs and symptoms (e.g., record only liver failure or hepatitis rather than jaundice, asterixis, and elevated transaminases). However, if a constellation of signs and/or symptoms cannot be medically characterized as a single diagnosis or syndrome at the time of reporting, it is acceptable to report the information that is currently available. If a diagnosis is subsequently established, it should be reported as follow-up information.

9.5.2.2 Deaths

All deaths that occur during the protocol-specified AE reporting period regardless of attribution, will be reported to the appropriate parties. When recording a death, the event or condition that caused or contributed to the fatal outcome should be reported as the single medical concept. If the cause of death is unknown and cannot be ascertained at the time of reporting, report "Unexplained Death".

9.5.2.3 Preexisting Medical Conditions

A preexisting medical condition is one that is present at the start of the study. Such conditions should be reported as medical and surgical history. A preexisting medical condition should be re-assessed throughout the trial and reported as an AE or SAE only if the frequency, severity, or character of the condition worsens during the study. When reporting such events, it is important to convey the concept that the preexisting condition has changed by including applicable descriptors (e.g., "more frequent headaches").

